# 5 INTERIM ANALYSIS

The IDMC for the MONETTE study is constituted to provide an independent, external, and unbiased assessment of safety, tolerability and efficacy during the conduct of the trial. The IDMC is an independent external group of experts and consists of two independent therapeutic area experts and a biostatistician with experience in the monitoring of randomised clinical studies. IDMC meetings consist of different sessions. In general, no information deemed to unblind attendees is presented or discussed during open session. Closed sessions are attended by the IDMC members and a very limited number of unblinded people including an independent statistician and data is presented and discussed in a manner that reveals treatment group details. Further information about the IDMC and the format of the IDMC meetings can be found in the IDMC charter.

# Interim Analysisco

The CCI interim analysis is conducted once approximately CCI subjects have been enrolled in total and had the opportunity for approximately CCI follow up. The CCI follow up enables RECIST scans for confirmation of response. The rationale for this approach is to ensure the objective response rate (ORR) is not artificially underestimated at an interim analysis e.g., if there are subjects ongoing treatment with unconfirmed response who are yet to have their confirmatory scan.

The IDMC may recommend to stop recruitment to the ceralasertib plus durvalumab treatment arm if there are  $\mathbf{r}$  or  $\mathbf{CCI}$  responses out of  $\mathbf{cCI}$  subjects, i.e.,  $ORR \leq \mathbf{cCI}$ %. This stop rule corresponds to  $< \mathbf{cCI}$ % predictive probability of success should recruitment continue to the end of the study. There is  $\mathbf{r}$ % risk to incorrectly stop if the true  $ORR = \mathbf{cCI}$ %.

The IDMC may recommend to stop recruitment to the ceralasertib monotherapy arm if there are responses out of subjects i.e., ORR = %. Should the combination treatment arm be terminated at the interim analysis, the monotherapy arm may also be terminated if there are for CCI responses out of subjects, i.e.,  $ORR \leq \%$  since in this situation it is unlikely to achieve the target ORR to warrant future development should it continue to the end of the study.

# Interim Analysisco

The **CCI** interim analysis is carried out once approximately **CCI** subjects have been enrolled in total and had the opportunity for approximately **CCI** weeks follow up. The **CCI** weeks follow up enables **RECIST** scans for confirmation of response and also preliminary characterisation of the durability of response, which is a key secondary endpoint.

The IDMC may recommend to stop recruitment to combination treatment arm at the CCI interim analysis if there are cci or cci responses out of cci subjects, i.e.,  $ORR \le cci$ %. The IDMC may recommend to stop recruitment to monotherapy treatment arm if there are cci or cci responses out of cci subjects i.e.,  $ORR \le cci$ % and the exact cci cci% CI for the proportion of subjects with non-progressive disease at week cci (Disease Control Rate) is < cci%. Should the combination treatment arm be terminated at the interim analysis, the

monotherapy arm may also be terminated if there are  $\overset{\text{cc}}{=}$  or  $\overset{\text{cc}}{=}$  responses out of  $\overset{\text{cc}}{=}$  subjects, i.e., ORR  $\leq \overset{\text{cc}}{=}$ % since in this situation it is unlikely to achieve the target ORR to warrant future development should it continue to the end of the study.

In addition to the ORR, the BOR is presented as well.

# LIST OF ABBREVIATIONS

Abbreviation or Specialized Term	Definition
ADA	Anti-Drug Antibody
AE	Adverse event
AESI	Adverse Event of Special Interest
ALT	Alanine Aminotransferase
ARID1A	AT-rich interactive domain-containing Protein 1A
AST	Aspartate Aminotransferase
ATM	Ataxia Telangiectasia Mutated
ATR	Ataxia Telangiectasia and Rad3-Related Protein
BILI	Total Bilirubin
BMI	Body mass index
BOR	Best Objective Response
BRAF	B-Rapidly Accelerated Fibrosarcoma Gene
BSR	Baseline Scaled Ratio
CI	Confidence Interval
COVID-19	Coronavirus Disease 2019
CR	Complete Response
CRF	Case Report Form
CSP	Clinical Study Protocol
CSR	Clinical Study Report
CTCAE	Common Terminology Criteria for AEs
CV	Coefficient of Variation
DCO	Data Cut-Off
DoR	Duration of Response
DRM	Data Review Meeting
ECG	Electrocardiogram
ECOG	Eastern Cooperative Oncology Group
GCP	Good Clinical Practice
gCV	Geometric Coefficient of Variance
Gmean	Geometric Mean
gSD	Geometric Standard Deviation
HR	Hazard Ratio
IO	Immune-Oncology

#### STATISTICAL ANALYSIS PLAN D533AC00001 – ed. 1.0

ICF	Informed Consent Form
IL	Item Library
IP	Investigational Product
IPD	Important Protocol Deviation
KIT	Proto-oncogene c-KIT
LDH	Lactic Acid Dehydrogenase
LLOQ	Lower Limit of Quantification
LVEF	Left Ventricular Ejection Fraction
MedDRA	Medical Dictionary for Regulatory Activities
max	Maximum
min	Minimum
MMRM	Mixed Model for Repeated Measures
MSI	Activating Mutations and Microsatellite Instability
MUGA	Multigated Acquisition
NA	Not Applicable
NE	Not Evaluable
NF1	Neurofibromatosis type 1
NTL	Non-Target Lesion
NR	Not Reportable
NRAS	NRAS proto-oncogene, GTPase
NS	No Sample
OAE	Other significant adverse event
ORR	Objective Response Rate
OS	Overall Survival
PD	Progressive Disease
PD-(L)1	Programmed Cell Death 1 Ligand
PFS	Progression Free Survival
РК	Pharmacokinetics
PR	Partial Response
РТ	Preferred Term
RDI	Relative Dose Intensity
SAE	Serious adverse event
SAP	Statistical Analysis Plan
SD	Stable Disease
SE	Standard Error
SMQ	Standardized MedDRA Queries

#### STATISTICAL ANALYSIS PLAN D533AC00001 – ed. 1.0

SOC	System Organ Class
Std Dev	Standard Deviation
TL	Target Lesion
TLF	Tables Listings Figures
TACE	Transarterial Chemoembolization
TARE	Transarterial Radioembolization
TEAE	Treatment Emergent Adverse Events
CCI	CCI
TOC	Table of Contents
TTR	Time to Objective Response
ULN	Upper Limit of Normal

# **AMENDMENT HISTORY**

CATEGORY Change refers to:	Date	Description of change	In line with CSP?	Rationale
N/A	Click or tap to enter a date.	Initial approved SAP for the biopsy sub-study	N/A	N/A

# **1 INTRODUCTION**

The purpose of this document is to give details for the statistical analysis of the biopsy substudy of D533AC00001 supporting the clinical study report (CSR). The reader is referred to the clinical study protocol (CSP) and the case report form (CRF) for details of study conduct and data collection. This statistical analysis plan (SAP) is based on Amendment *2* of the CSP dated 14 March 2022. In the event of future amendments to the protocol, this SAP may be modified to account for changes relevant to the statistical analysis.

A separate SAP was created for the main study. There are no plans to pull clinical data for efficacy from the main study and the sub-study.

# 2 CHANGES TO PROTOCOL PLANNED ANALYSES

Not applicable.

# **3** DATA ANALYSIS CONSIDERATIONS

# **3.1** Timing of Analyses

The details of the analyses planned during the conduct of this study are outlined below and summarised in the following table.

#### Table 1: Summary of planned analyses

Analysis	Trigger	Scope
Primary Analysis	Once all enrolled subjects have had a minimum of months of follow-up after start of study intervention or have discontinued from the study, whichever occurs first.	All available data
CCI Analysis	Once % of the subjects have died or % months after last subject is enrolled, whichever is the earliest event.	All available data

DCO: Data cut-off

The primary analysis for the biopsy sub-study is conducted once all enrolled subjects have had a minimum of months of follow-up after start of study intervention or have discontinued from the study, whichever occurs first. At this primary analysis the CSR for

the biopsy sub-study is written, which may be finalised after the CSR is finalised for the main study. A CCI analysis is performed either CCI months after the last subject is enrolled, or CCI% of subjects have died, whichever is the earlier event.

# **3.2** General Considerations

The below-mentioned general principles will be followed throughout the study:

- Descriptive statistics will be used for all variables, as appropriate.
  - Continuous variables will be summarised by the number of observations, mean, standard deviation, median, upper, and lower quartiles where indicated, minimum and maximum. For log-transformed data (ie, pharmacokinetic [PK] concentration data) it is more appropriate to present geometric mean, coefficient of variation (CV), median, minimum, and maximum.
  - If data are available for less than 3 subjects, no summary statistics other than minimum, maximum and number of observations are presented.
  - Categorical variables will be summarised by frequency counts and percentages for each category. Unless otherwise stated, percentages will be calculated based on the analysis set population and by timepoint as appropriate.
- For continuous data, the mean, standard deviation, and median are rounded to one additional decimal place compared to the original data. Minimum and maximum are displayed with the same accuracy as the original data.
- Time-to-event variables will be presented using the Kaplan-Meier (KM) methodology, including median time calculated from the KM curves.
- For categorical data, percentages are rounded to one decimal place with the exception of 100% which is presented as a whole number.
- SAS® version 9.4 (or higher) and/or other validated software (as appropriate) will be used for the analyses. In case R is used, the R build version and the version of each used R package will be documented.

# 3.2.1 Sample Size Determination

Approximately patients are planned to be enrolled such that approximately 30 patients have at least 2 evaluable paired biopsies (at the baseline and off ceralasertib treatment) including at least 15 patients with at least 3 evaluable biopsies (at baseline, on ceralasertib treatment and off ceralasertib treatment).

Sample sizing is based on expected fold increase in CD8+ T-cells infiltration. The fold assumption represents the observed increase in proliferating CD8+ T-cells infiltration in

association with Pembrolizumab and Nivolumab or Nivolumab/Ipilimumab efficacy inmelanoma (Tumeh et al, 2014; Grasso et al, 2020).

The sample size of 30 evaluable patients is expected to give adequate sample size to assess changes of CD8+ T-cells from baseline.

# 3.2.2 Study Treatment

During Cycle 0, patients will be treated with ceralasertib 240 mg BD, as oral tablets, from Days 1 to 7, Q28D, followed by an off-treatment period between Days 8 to 28 (i.e. no-dose period). From Cycle 1, patients will be treated with the combination of ceralasertib 240 mg BD, oral tablets, from Days 1 to 7, plus durvalumab 1500 mg Day 8, as an IV infusion, Q28D, until progressive disease (confirmed RECIST 1.1-defined radiological progression), unacceptable toxicity, withdrawal of consent, or if a study treatment discontinuation criterion is met.

# 3.2.3 Baseline

In general, the last observed measurement prior to first dose of study intervention will be considered the baseline measurement.

For assessments on the day of first dose where time is not captured, a nominal pre-dose indicator, if available, serves as sufficient evidence that the assessment occurred prior to first dose. Assessments on the day of the first dose where neither time nor a nominal predose indicator are captured is considered prior to the first dose if such procedures are required by the protocol to be conducted before the first dose. If no value exists before the first dose/administration, then the baseline value is treated as missing.

For clinical data, if two measurements are equally eligible to assess patient status at baseline (e.g., two assessments both on the same date with no time recorded), the average is used as the baseline value. For non-numeric laboratory tests (ie, some of the urinalysis parameters) where taking the average is not possible, the best value (value closest to none/normal/negative) is used as baseline as this is most conservative. In the scenario where there are two eligible baseline assessments recorded on the same day, one with time recorded and the other without time recorded, the one with the time recorded is selected as baseline. Where safety data will be summarised over time, time on study is calculated in relation to date of first treatment.

In all summaries change from baseline variables are calculated as the post-treatment value minus the value at baseline. The percentage change from baseline is calculated as (post-baseline value - baseline value)/(baseline value) x 100. For any endpoint subjected to log transformation, the change from baseline calculated and summarised on the log scale are back-transformed and presented as a 'baseline scaled ratio' (BSR). Percentage change is then calculated as (BSR - 1)  $\times$  100.

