#### **3.2.2** Study Treatment

The main study is a Phase 2, randomised, open-label, multicentre, international study assessing the efficacy and safety of ceralasertib and ceralasertib plus durvalumab in subjects with unresectable or advanced melanoma and primary or secondary resistance to programmed death-ligand 1 [PD-(L)1] inhibition. Approximately 150 subjects are randomised, at a 2:1 randomisation ratio (approximately 100 subjects in Arm 1 and approximately 50 subjects in Arm 2) to the following intervention groups:

- Arm 1: Ceralasertib 240 mg BD oral tablets, from Days 1 to 7 plus durvalumab 1500 mg Day 8, IV infusion, Q28D, until progressive disease, (confirmed RECIST 1.1-defined radiological progression), unacceptable toxicity, withdrawal of consent, or if a study treatment discontinuation criteria is met.
- 2. Arm 2: Ceralasertib 240 mg BD oral tablets, from Days 1 to 7, Q28D, until progressive disease, (confirmed RECIST 1.1-defined radiological progression), unacceptable toxicity, withdrawal of consent, or if a study treatment discontinuation criterion is met.

Crossover within the study is not be permitted. There is no defined maximum treatment duration for the treatment arms as the subjects receive study treatment until progressive disease (RECIST 1.1-defined radiological progression), unacceptable toxicity, withdrawal of consent, or if a study treatment discontinuation criterion is met.

Randomisation into the treatment arms is stratified by:

• Resistance to prior immune-oncology treatment (primary/early relapse in adjuvant setting vs secondary resistance).

• Baseline lactate dehydrogenase (LDH) expression (below and equal to the upper limit of normal vs above upper limit of normal).

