#### Actual duration of exposure (weeks)

- Actual exposure to ceralasertib [months] = total exposure to ceralasertib total duration of dose interruptions and dose delays
- Actual exposure to durvalumab [months] = total exposure to durvalumab total duration of dose delays

The total duration of dose delays is defined as any length of time in addition to the planned cycle length where the patient has not taken/received any of the planned doses.

- Definition of dose delay for ceralasertib: if the number of days between Day 1 of a cycle and Day 1 of the previous cycle is > 28 days, then the number of additional days above 28 days is the duration of delay.
- Definition of dose delay for durvalumab: for Cycle 1, if the number of days between the first administration of durvalumab on Day 8 and the first administration of ceralasertib on Day 1 is > 7 days, then the number of additional days above 7 days is the duration of the delay. For all subsequent cycles, if the number of days between Dayo8 of a cycle and Day 8 of the previous cycle is > 28 days, then the number of additional days above 28 days is the duration of delay.

The total duration of dose interruption is defined as any length of time during the cycle where the patient has not taken/received any of the planned doses.

• Definition of dose interruptions for ceralasertib: the total number of full-day treatment interruptions, including missed and forgotten doses. Half-day interruptions are not considered in the actual treatment exposure derivation

Note: In case the last days of cycle doses of ceralasertib are not taken (eg, Day 7) and no further medication will be taken, this is an interruption but will not be included in the total duration of dose interruptions as the total treatment exposure already includes this reduction via "date of last dose where dose > 0 mg".

The calculation of actual exposure makes no adjustment for any dose reductions that may have occurred.

Missed and forgotten doses should be recorded as a dose interruption with the reason recorded as "Patient forgot to take dose". These missed or forgotten doses are not included as dose interruptions in the summary tables, but the information appears in the listing for dosing. However, these missed and forgotten doses are considered in the derivation of actual exposure.

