# 4.6 Immunogenicity

Immunogenicity results are listed for each subject and summarised for the Safety analysis set. Number and percentage of subjects in the following categories are provided.

- Anti-drug antibody (ADA) positive at baseline and/or post-baseline visits.
- Persistent positive, defined as positive at ≥2 post-baseline assessments (with ≥16 weeks between first and last positive) or positive at last post-baseline assessment.
- Transient positive, defined as negative at last post-baseline assessment and positive at only one post-baseline assessment or at ≥2 post-baseline assessments (with <16 weeks between first and last positive).
- Treatment-boosted, defined as baseline positive ADA titre that was boosted to a 4-fold or higher level following drug administration.

All valid assay results from subjects who receive any study drug are included in immunogenicity summaries. Blood samples collected outside of the protocolled window are summarised at the closest nominal time point that does not already have a value. All subjects with titre information are shown in the data listing.

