#### 3.2.5 Visit Window

For safety, time windows are defined for any presentations that summarise values by visit. The following conventions apply:

- For safety data study day reference is date of first dose of study treatment as Day 1, for PK the reference is the time of study treatment administration on the day PK blood samples are taken, for efficacy data study day references date of first dose as Day 1.
- The time windows are exhaustive so that data recorded at any timepoint has the potential to be summarised. Inclusion within the time window are based on the actual date and not the intended date of the visit.
- All unscheduled visit data have the potential to be included in the summaries.
- The window for the visits following baseline are constructed in such a way that the upper limit of the interval falls half way between the two visits (the lower limit of the first post-baseline visit is Day 2). If an even number of days exists between two consecutive visits then the upper limit will be taken as scheduled visit day + (duration between scheduled visits)/2. (i.e. don't apply the minus 1 day).
- Subjects may delay durvalumab dosing under certain circumstances.
  - Dosing may be delayed per the Dosing Modification and Toxicity Management Guidelines, due to either an immune or a non-immune-related AE.
  - If dosing must be delayed for reasons other than treatment-related toxicity, dosing will resume as soon as feasible.
  - Dosing intervals of subsequent cycles may be shortened as clinically feasible in order to gradually align treatment cycles with the schedule of tumour efficacy (RECIST) assessments.
- Visit windowing is done separately for each assessment based on the schedule of events specific to that assessment.

- Should Study Day be missing (due to partial dates), then visit is assigned to the nominal visit at which that assessment was recorded, and no windowing will be performed for that specific assessment.
- Visit windowing is conducted up to and including the "Last dose of study treatment" visit. That is, the "Last dose of study treatment" visit is reassigned to a scheduled visit based on the study day that visit occurred at.
- For summaries showing the maximum or minimum values, the maximum/minimum value recorded on treatment are used (regardless of where it falls in an interval).
- Listings display all values contributing to a time point for a subject.

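### Anti-drug antibody (ADA) baseline is tied to the first ceralasertib dose, so ADA samples taken before the first durvalumab infusion can count as post-baseline

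*SAP*

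**What the plan says.** Section 3.2.3 of the main-study SAP and section 3.2.3 of the sub-study SAP carry the same default: "In general, the last observed measurement prior to first dose of study intervention will be considered the baseline measurement". Both add "If no value exists before the first dose/administration, then the baseline value is treated as missing". The main-study SAP makes one exception, for efficacy variables, which are anchored on randomisation. Neither SAP makes an exception for ADA.

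Section 4.6 of each SAP then sorts ADA results by baseline and post-baseline status:

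- positive at baseline and/or post-baseline;
- persistent positive: at least two post-baseline positives with 16 weeks or more between first and last, or positive at the last post-baseline assessment;
- transient positive: negative at the last post-baseline assessment, with one post-baseline positive, or several within less than 16 weeks;
- "Treatment-boosted, defined as baseline positive ADA titre that was boosted to a 4-fold or higher level following drug administration".

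The drug in that last definition is not named. Section 4.6 also takes in valid results from subjects who received any study drug.

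Dosing is sequential. Main-study section 3.2.2 gives Arm 1 ceralasertib "from Days 1 to 7 plus durvalumab 1500 mg Day 8, IV infusion, Q28D". In section 3.2.2 of the sub-study SAP, Cycle 0 is ceralasertib on Days 1 to 7 and then no dosing to Day 28. Durvalumab first appears on Day 8 of Cycle 1.

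**The concern.** The antibodies summarised alongside an infused checkpoint inhibitor are meant to show what happened after that agent was given, against what was there before. The dividing line should therefore be the first durvalumab infusion. The written default puts it at the first dose of any study intervention, which is ceralasertib.

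Every sample between the two dates is then on the wrong side. Three of the four ADA categories depend directly on that line. A pre-existing antibody found in the gap can be reported as a post-baseline positive in a subject not yet exposed to durvalumab, and a pre-drug titre drawn on the infusion day cannot serve as the reference for boosting.

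**Working it through.** **1. The gap between first ceralasertib and first durvalumab**

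- Main study, Arm 1: Day 8 − Day 1 = 7 days. This reproduces the plan's own figure. The exposure section counts a Cycle 1 durvalumab delay only when the interval between "the first administration of durvalumab on Day 8 and the first administration of ceralasertib on Day 1 is > 7 days".
- Sub-study, counted from Cycle 0 Day 1: first durvalumab falls on study day 28 + 8 = 36, so the gap is 36 − 1 = 35 days.
- Cycle 0 does count as first dose in the sub-study. Section 3.2.4 includes it in the on-treatment definition, and section 4.3.14.2.1 starts treatment-emergent adverse events from the first administration in Cycle 0.
- Arm 2 of the main study receives no durvalumab, so the main-study gap concerns Arm 1 only.

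**2. Classifying pre-infusion samples under each anchor**

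The first post-baseline window opens on Day 2 (section 3.2.5 in both SAPs).

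| Sample, all before any durvalumab | Written rule | First-durvalumab anchor |
|---|---|---|
| Screening, or Day 1 before ceralasertib | baseline | baseline-eligible |
| Main study Arm 1, Days 2 to 8 | post-baseline | baseline-eligible |
| Sub-study, Days 2 to 36 | post-baseline | baseline-eligible |

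**3. What this does to the rows of section 4.6**

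- *Only pre-infusion sample is on the infusion day.* Baseline is missing, so treatment-boosted cannot be assessed for that subject.
- *Positive in the gap, no later sample.* The subject is positive at the last post-baseline assessment and so is persistent positive, without post-infusion data.
- *Positive in the gap, negative at every later sample.* The subject is transient positive. Under a durvalumab anchor the same subject is baseline positive only.
- *Positive in the gap and again after infusion, negative at the last sample.* The row can change, because the span starts earlier. Sixteen weeks is 16 × 7 = 112 days. Counted from a positive on Day 2, it is reached on Day 2 + 112 = 114. Counted from the first infusion day, it is reached on Day 8 + 112 = 120 (main study) or Day 36 + 112 = 148 (sub-study). The span can therefore begin up to 8 − 2 = 6 days, or 36 − 2 = 34 days, before exposure.
- *Positive at baseline and/or post-baseline, taken together.* The total is the same under either anchor.

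**4. How many subjects**

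This cannot be computed from the SAPs, which do not give the ADA sampling days. If no sample falls in the gap, nobody is affected. If the only pre-infusion sample is taken on the day of first infusion, every durvalumab-treated subject is affected, which in Arm 1 is about 100 by the planned size.

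**The case against.** The best reply is that the harm depends on a schedule not shown. If the protocol takes ADA at screening or before dosing on Day 1, the result is baseline under both anchors and nothing changes. The default also opens with a qualifier that allows exceptions. Section 3.2.5 windows each assessment on its own schedule, and a reader would naturally take the drug in the boosting definition to be the one the antibody is directed against. On that view this is a clarification, in a summary that feeds no test, interim rule or efficacy endpoint.

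Much of this stands, and it sets the priority. It does not remove the point: no exception is written, so a programmer who follows the text will use first ceralasertib. Section 3.2.5 also allows durvalumab to be delayed, which lengthens the gap.

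A reader might be tempted to go further in four ways that the documents do not support:

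- *The exposure sections prove the anchor.* They do not. Their note on first dose belongs to the exposure formula, and the sub-study exposure section leaves Cycle 0 out.
- *PK was given its own baseline and ADA was not.* The sentence "for PK the reference is the time of study treatment administration on the day PK blood samples are taken" sets a time reference for windowing. It is not a baseline exception.
- *Treatment-emergent ADA counts will be inflated by a definite number.* Section 4.6 has no treatment-emergent row. Its persistent and transient rows do not require a negative baseline, so a subject who stays positive after infusion appears there under either anchor.
- *Post-infusion samples will be moved into an empty baseline slot.* The rule "Blood samples collected outside of the protocolled window are summarised at the closest nominal time point that does not already have a value" does not expressly forbid it, but it would need an unusual off-window sample, and section 3.2.3 already says such a baseline is missing.

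**Conclusion.** The point holds as a definition that misclassifies any ADA sample taken after first ceralasertib and before first durvalumab. The window is 7 days in Arm 1 of the main study and 35 days in the sub-study, as planned. Within it, baseline may be lost, treatment-boosted may become unassessable, a subject positive only before exposure may be called transient or persistent, and the persistence span may start up to 6 or 34 days early.

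The size in subjects is open, from none to all those treated with durvalumab. The conclusion rests on reading the default literally and on counting Cycle 0 as first dose, which the sub-study SAP does for on-treatment data and adverse events. The immunogenicity output is counts, percentages and listings, and the primary endpoints are untouched. It is worth correcting before programming, at modest priority.

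**What to change.** In sections 3.2.3 and 4.6 of both SAPs, add: *For ADA, baseline is the last valid result before the first durvalumab infusion; post-baseline is any valid result after it.* In the treatment-boosted definition, name durvalumab as the drug administered.

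As an optional safeguard, state that an out-of-window ADA sample is assigned only to a nominal time point on its own side of the first durvalumab infusion.

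The cost is two wording changes per SAP and one reference date in the ADA programming. No new data are needed and dosing is unaffected. If the protocol schedule puts no sample in the gap, the results do not change.
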